5.8.3. Pharmacodynamics / Biomarker Analyses

Changes in the concentration and proportion of subjects with abnormalities of individual pharmacodynamic biomarkers from baseline to the selected post treatment time points will be summarized. These include but are not limited to antinuclear antibody, anti-phospholipid antibodies, anti-ds-DNA, C3 and C4 complement, Cystatin C, IgA, IgG, and IgM.

It should be noted that a separate pharmacodynamics / biomarker report will be produced and associated analyses of serum, cellular and whole blood gene expression will be reported in that document.

5.8.4. Pharmacokinetic/Pharmacodynamic Relationships

If deemed feasible and necessary, exposure-response analyses may be performed. The analysis methods may be summarized in a separate analysis plan. Results of such analyses may be presented in a separate technical report.

5.8.5. Definition of Subgroups

To evaluate the consistency of the primary efficacy endpoint (proportion of participants with achieving at least 50% decrease in proteinuria from baseline at Week 24) subgroup analyses may be performed when the number of participants in the subset permits (at least 5 participants for each treatment group within a subset).

The subgroups for subgroup analysis may include, but are not limited to, the following:

1. Demographic subgroups

Subgroup	Variant	Definition
Region	1	Define based on UN guidance as per the M49 standard 
 • Asia Pacific • North America • Latin America • Europe
Age Group	1	
 • <55 • ≥55
Body Mass Index (BMI)	1	
 • normal <25 kg/m² • overweight 25-<30 kg/m² • obese ≥30 kg/m²
Body Weight Group	1 (Quartiles)	•
Race	1	
 • White • Black • Asian • All other categories
Ethnicity	1	
 • Hispanic or Latino • Not Hispanic or Latino
Gender	1	
 • Male • Female
Participants age at LN diagnosis	1	
 • < 21 years • ≥ 21 years

2. Disease Characteristics subgroups

Subgroup	Variant	Definition
Renal biopsy classes		
 • III • III + V • IV • IV + V
Nephrotic proteinuria defined as urine P/C ratio of ≥3	1	
 • UPCR <3 • UPCR ≥3
	2	
 • < Median • ≥ Median
eGFR		
 • eGFR ≥ 90 • eGFR ≥ 60 and < 90 • eGFR ≥ 30 and < 60 • eGFR < 30
SLEDAI-2K Score		
 • < Median • ≥ Median
PGA Score		
 • < Median • ≥ Median
Serologic status individually and collectively for anti-dsDNA, C3 and C4		

Subgroup	Variant	Definition
(i) dsDNA (positive, negative)		
 • Positive • Negative
(ii) Complement C3, C4		
 • Normal • Abnormal

3. Prior Medication subgroups

Subgroup	Variant	Definition
Glucocorticoids only		Yes or No
Glucocorticoids + Antimalarials		Yes or No
Glucocorticoids + Immunosuppressants		Yes or No
Glucocorticoids + Ace-inhibitors		Yes or No
Antimalarials + Immunosuppressants		Yes or No
Antimalarials + Ace-inhibitors		Yes or No
Immunosuppressants + Ace-inhibitors		Yes or No
Glucocorticoids + Antimalarials + Immunosuppressants		Yes or No
Glucocorticoids + Antimalarials + Ace-inhibitors		Yes or No
Antimalarials + Immunosuppressants + Ace-inhibitors		Yes or No
Glucocorticoids + Antimalarials + Immunosuppressants + Ace-inhibitors		Yes or No

5.9. Interim Evaluations

Early Termination Note: Due to the Sponsor's decision to stop screening of new participants as a result of enrollment challenges, fewer than 60 participants will be enrolled in the study. The end of study will occur after all enrolled participants have completed the Week 20 visit or discontinued study intervention prior to Week 24, and all participants have completed their final efficacy and safety visits per the SoA.

The first interim efficacy evaluation occurred on December 28, 2021. Due to early termination of the study, the second and third interim efficacy evaluations will not be performed.

Details of the Data Monitoring Committee (DMC) safety reviews and interim analysis assessments are included in a separate DMC Charter and DMC SAP. The DMC SAP contains definitions of analysis sets, derived variables, scope and objects of the DMC, data-cutoff points, statistical methods and output to be produced for the safety reviews and evaluation of efficacy as required by the DMC Charter. Additionally, a dedicated DMC Data Presentation Specifications (DPS) document details output and programming specifications.

The follow offers a high-level summary of the DMC activities.

5.9.1. Interim Efficacy Evaluations

Three interim efficacy evaluations will be conducted, when approximately 10, 25 and 40 participants respectively complete the Week 24 visit. The first interim efficacy evaluation is contingent to occur prior to the first participant entering the long-term extension, based on enrollment, that is when ~10 participants complete the Week 24 visit.

It should be noted that the first interim efficacy evaluation will occur 2 months prior to the first patient entering the LTE. It is projected that at that time, ~10 participants will complete the Week 24 visit. If enrollment is expedited and as many as ~25 patients reach the Week 24 visit instead, then the first and second interim efficacy evaluations will be combined. Otherwise, the first and second interim efficacy evaluation will occur separately. This decision to combine the first and second interim efficacy evaluation will be made ~4 months prior to the first patient entering LTE.

The DMC will review the unblinded efficacy data and make observations about the next step of study/program conduct, based upon the results of the interim efficacy evaluations.

The primary endpoint will be used for the interim efficacy evaluations.

A Bayesian predictive analysis based on a beta-binomial distribution on longitudinal data will be used for the analysis at each evaluation. At each of the three interim efficacy evaluations, if the predictive probability of success at the end of the study (the 1-sided p-value from the difference in proportion of participants with $\geq 50\%$ decrease in proteinuria between the guselkumab and placebo intervention groups is less than a 1-sided alpha of 10%), given the current results, is $< 10\%$ then the futility criteria would be met.

5.9.1.1. First Interim Efficacy Evaluation

At the first interim efficacy evaluation meeting (prior to the first participant entering the long-term extension, when approximately 10 participants complete their Week 24 visit), the DMC will examine efficacy for futility of advancing to the long-term extension based upon the predictive probability of success of the study given the available data up to Week 24 at that point. The possible recommendations of the DMC concerning efficacy at the first meeting include:

1. **Criteria for evidence for futility was met.** If the futility criterion is met, the DMC will recommend not advancing to the long-term extension of the study.
2. **Criteria for evidence of futility was NOT met.** If the futility criterion is not met, the DMC will recommend the participants that qualify continue to advance to the long-term extension of the study.

5.9.1.2. Second and Third Interim Efficacy Evaluation

At the second and third DMC interim efficacy evaluation (when approximately 25 and 40 participants, respectively, complete their Week 24 visit), the DMC will examine efficacy for futility based on the predictive probability of success given the available data up to Week 24 at that point. The possible observations of the DMC concerning efficacy at the second and third meeting include:

1. **Criteria for evidence of futility was met.** If the futility criterion is met, the DMC will recommend to stop the study. Furthermore, the DMC will recommend to stop enrollment of additional participants due to futility if all planned participants have not been enrolled.

2. **Criteria for evidence of futility was not met.** If the futility criterion is not met, the DMC will recommend continuing the study.

Details are outlined in the DMC SAP.

5.9.2. Data Monitoring Committee

The independent DMC will monitor data on an ongoing basis to ensure the continuing safety of the participants enrolled in the study. The committee will meet periodically to review interim data. After the review, the DMC will make recommendations regarding the continuation of the study. Any safety concerns will be communicated to the Sponsor Committee Chairperson.

None of the DMC members will be participating in the study; they will be independent of the Sponsor. The independent DMC consists of 2 medical experts in relevant therapeutic areas and 1 statistician and are to be specified before study initiation. The major function of the DMC is to monitor the safety of the study intervention, to evaluate efficacy data and provide recommendations for placing the study on hold or stopping the study in the event of serious safety concerns or futility.

Periodic safety reviews will occur as outlined in the DMC Charter, initiating when the 5th participant has been randomized or 3 months after the first participant is dosed, whichever comes first. Subsequent meetings will occur approximately every 4 months until the last meeting which will be within 6 months of the Week 60 DBL.

Serious adverse events will be reported to the DMC members on an ongoing basis. The DMC will have access to the unblinded data and review tabulated safety summaries (if appropriate) and any additional safety data that the DMC may request.

The content of the safety summaries and interim efficacy evaluations, the DMC roles and responsibilities and the general procedures (including communication plan) and their possible recommendations on study conduct will be defined and documented in the DMC Charter prior to the first DMC review.

REFERENCES

FACIT. www.facit.org. Accessed 01 Oct 2017.

Guy W (1976), Ed. ECDEU Assessment Manual for Psychopharmacology. Rockville, MD: US Department of Health, Education, and Welfare Public Health Service Alcohol, Drug Abuse, and Mental Health Administration, 1976:217-222.

MCID	minimum clinically important differences
MedDRA	Medical Dictionary for Regulatory Activities
Mg	milligram
MI	multiple imputation
MMF	mycophenolate mofetil
MMRM	mixed effects repeated measures model
MPA	mycophenolic acid
NSAIDs	nonsteroidal anti-inflammatory drug
PBMC	peripheral blood mononuclear cell

PD	pharmacodynamic(s)
PGA	Physician's Global Assessment of Disease Activity
PGIC	Patient Global Impression of Change
PK	pharmacokinetic(s)
q4w	every 4 weeks
SAE	serious adverse event
SAP	Statistical Analysis Plan
SC	subcutaneous
SD	standard deviation
SLE	systemic lupus erythematosus
SLEDAI-2K	Systemic Lupus Erythematosus Disease Activity Index 2000
SoA	Schedule of Activities
TF	treatment failure
ULN	upper limit of normal
UPCR	Urine Protein Creatinine Ratio
V	volume distribution
WBC	white blood cell
WHO-DD	World Health Organization Drug Dictionary

APPENDIX 2: CHANGES TO PROTOCOL-PLANNED ANALYSES

N/A

APPENDIX 3: DEMOGRAPHICS AND BASELINE CHARACTERISTICS

The number of participants in each analysis set will be summarized and listed by intervention group, and overall. In addition, the distribution of participants by region, country, and site ID will be presented unless otherwise noted.

Table 5 presents a list of the demographic variables that will be summarized by intervention group, and overall for the FAS analysis set(s). Demographics will also be summarized by region using the FAS analysis set. Table 6 presents the baseline disease characteristics variables that will be summarized by intervention group and overall for the FAS analysis set(s).

Table 5: Demographic Variables

Continuous Variables:	Summary Type
Age (years)	Descriptive statistics (N, mean, standard deviation [SD], median and range [minimum and maximum], and IQ range).
Weight (kg)	
Height (cm)	
Body Mass Index (BMI) (kg/m ²)	
Categorical Variables	
Age (<55 years, and ≥55 years])	Frequency distribution with the number and percentage of participants in each category.
Sex (male, female)	
Race ^a (American Indian or Alaska Native, Asian, Black or African American, Native Hawaiian or other Pacific Islander, White, Multiple)	
Ethnicity (Hispanic or Latino, not Hispanic or Latino)	
BMI ([normal <25 kg/m ² , overweight ≥25 kg/m ²])	

Table 6: Baseline Disease Characteristics Variables

Continuous Variables:	Categories	Summary Type	
Proteinuria (urine P/C ratio) (mg/mg)		Descriptive statistics (N, mean, standard deviation [SD], median and range [minimum and maximum], and IQ range).	
eGFR (mL/min/m ²)			
SLEDAI-2K score (0-105)			
PGA score (0-3)			
Active joints with both pain and inflammation (0-28)			
Number of joints with pain (only) (0-28)			
Number of joints with swelling (only) (0-28)			
CLASI Damage Score (0-56)			
CLASI Activity Score (0-70)			
Lupus Quality of Life (LupusQOL) score and individual domains			
FACIT-Fatigue score			
Lupus Symptoms:			
Joint pain scale (0-10)			
Joint stiffness scale (0-10)			
Rash scale (0-10)			
Swelling scale (0-10)			
LN duration			
SLE duration			
Categorical Variables			Frequency distribution with the number and percentage of participants in each category.
LN Flare	
 • Yes • No 		
Renal biopsy classes	
 • III • III + V • IV • IV + V 		
Nephrotic proteinuria defined as urine P/C ratio of ≥ 3	
 • UPCR < 3 • UPCR ≥ 3 		
eGFR	
 • eGFR ≥ 90 • eGFR ≥ 60 and < 90 • eGFR ≥ 30 and < 60 • eGFR < 30 		
dsDNA (positive, negative)	
 • Positive • Negative 		
Complement C3, C4	
 • Normal • Abnormal 		

APPENDIX 4: PROTOCOL DEVIATIONS

In general, the following list of major protocol deviations may have the potential to impact participants' rights, safety or well-being, or the integrity and/or result of the clinical study. Participants with major protocol deviations will be identified prior to DBL and the participants with major protocol deviations will be summarized by category.

- Developed withdrawal criteria but not withdrawn
- Entered but did not satisfy criteria
- Received a disallowed concomitant treatment
- Received wrong treatment or incorrect dose
- Other
 - Missed visit/assessment due to COVID-19

APPENDIX 5: PRIOR AND CONCOMITANT MEDICATIONS

Prior and Concomitant medications will be coded using the World Health Organization Drug Dictionary (WHO-DD). Prior medications are defined as any therapy used before the day of first dose (partial or complete) of study intervention. Concomitant medications are defined as any therapy used on or after the same day as the first dose of study intervention, including those that started before and continue on after the first dose of study intervention.

Summaries of concomitant medications will be presented by anatomic and therapeutic class (ATC) term, and intervention group. The proportion of participants who receive each concomitant medication will be summarized as well as the proportion of participants who receive at least 1 concomitant medication. In addition, concomitant medications of special interest will be presented.

Prior medications will be summarized by intervention group and ATC term.

APPENDIX 6: MEDICAL HISTORY

Medical history of lupus and body system will be listed and summarized by intervention groups.

APPENDIX 7: INTERVENTION COMPLIANCE

Compliance will be summarized descriptively for each study intervention. Compliance to randomized intervention versus actual intervention will be presented in a summary table.

APPENDIX 8: ADVERSE EVENTS OF SPECIAL INTEREST

N/A

APPENDIX 9: MEDICATIONS OF SPECIAL INTEREST

N/A

APPENDIX 10: LABORATORY TOXICITY GRADING

The grading scale used for lab assessments is based on ‘Common Terminology Criteria for Adverse Events (CTCAE) v5.0’.

If a laboratory value falls within the grading as specified below but also within the local laboratory normal limits, the value is considered to be normal and will be reset to grade 0.

Pre-baseline measurements will use the same grading ranges as applied to baseline measurements. In case a test has two sets of ranges – one for baseline normal and one for baseline abnormal, the one for baseline normal will be applied for all measurements taken pre-baseline and on baseline.

Text in gray italic in the table is present in the grading scale, but is not applied by Janssen when grading lab data.

CTCAE Term	Grade 1	Grade 2	Grade 3	Grade 4	Janssen implementation notes
Blood and lymphatic system disorders					
Anemia	Hemoglobin (Hgb) <LLN - 10.0 g/dL; <LLN - 6.2 mmol/L; <LLN - 100 g/L	Hemoglobin (Hgb) <10.0 - 8.0 g/dL; <6.2 - 4.9 mmol/L; <100 - 80g/L	Hemoglobin (Hgb) <8.0 g/dL; <4.9 mmol/L; <80 g/L; transfusion indicated	Life-threatening consequences; urgent intervention indicated	Clinical signs and symptoms are not taken into consideration for grading.
Leukocytosis	-	-	>100,000/mm ³ ; >100 x 10e9 /L	Clinical manifestations of leukocytosis; urgent intervention indicated	Clinical signs and symptoms are not taken into consideration for grading; Added ranges in SI unit (x 10e9 /L)
Investigations					
Activated partial thromboplastin time prolonged	>ULN - 1.5 x ULN	>1.5 - 2.5 x ULN	>2.5 x ULN; bleeding	-	Clinical signs and symptoms are not taken into consideration for grading.
Alanine aminotransferase increased	>ULN - 3.0 x ULN if baseline was normal; 1.5 - 3.0 x baseline if baseline was abnormal	>3.0 - 5.0 x ULN if baseline was normal; >3.0 - 5.0 x baseline if baseline was abnormal	>5.0 - 20.0 x ULN if baseline was normal; >5.0 - 20.0 x baseline if baseline was abnormal	>20.0 x ULN if baseline was normal; >20.0 x baseline if baseline was abnormal	Ranges defined for "abnormal baseline" are applied only if baseline > ULN. If baseline < LLN, then ranges for "normal baseline" are applied.
Alkaline phosphatase increased	>ULN - 2.5 x ULN if baseline was normal; 2.0 - 2.5 x baseline if baseline was abnormal	>2.5 - 5.0 x ULN if baseline was normal; >2.5 - 5.0 x baseline if baseline was abnormal	>5.0 - 20.0 x ULN if baseline was normal; >5.0 - 20.0 x baseline if baseline was abnormal	>20.0 x ULN if baseline was normal; >20.0 x baseline if baseline was abnormal	Ranges defined for "abnormal baseline" are applied only if baseline > ULN. If baseline < LLN, then ranges for "normal baseline" are applied.
Aspartate aminotransferase increased	>ULN - 3.0 x ULN if baseline was normal; 1.5 - 3.0 x baseline if baseline was abnormal	>3.0 - 5.0 x ULN if baseline was normal; >3.0 - 5.0 x baseline if baseline was abnormal	>5.0 - 20.0 x ULN if baseline was normal; >5.0 - 20.0 x baseline if baseline was abnormal	>20.0 x ULN if baseline was normal; >20.0 x baseline if baseline was abnormal	Ranges defined for "abnormal baseline" are applied only if baseline > ULN. If baseline < LLN, then ranges for "normal baseline" are applied.

CTCAE Term	Grade 1	Grade 2	Grade 3	Grade 4	Janssen implementation notes
Blood bilirubin increased	>ULN - 1.5 x ULN if baseline was normal; > 1.0 - 1.5 x baseline if baseline was abnormal	>1.5 - 3.0 x ULN if baseline was normal; >1.5 - 3.0 x baseline if baseline was abnormal	>3.0 - 10.0 x ULN if baseline was normal; >3.0 - 10.0 x baseline if baseline was abnormal	>10.0 x ULN if baseline was normal; >10.0 x baseline if baseline was abnormal	Ranges defined for "abnormal baseline" are applied only if baseline > ULN. If baseline < LLN, then ranges for "normal baseline" are applied.
CD4 lymphocytes decreased	<LLN - 500/mm ³ ; <LLN - 0.5 x 10e9/L	<500 - 200/mm ³ ; <0.5 - 0.2 x 10e9/L	<200 - 50/mm ³ ; <0.2 x 0.05 - 10e9/L	<50/mm ³ ; <0.05 x 10e9/L	
Cholesterol high	>ULN - 300 mg/dL; >ULN - 7.75 mmol/L	>300 - 400 mg/dL; >7.75 - 10.34 mmol/L	>400 - 500 mg/dL; >10.34 - 12.92 mmol/L	>500 mg/dL; >12.92 mmol/L	
CPK increased	>ULN - 2.5 x ULN	>2.5 x ULN - 5 x ULN	>5 x ULN - 10 x ULN	>10 x ULN	
Creatinine increased	Creatinine Kinase >ULN - 1.5 x ULN	Creatinine Kinase >1.5 - 3.0 x baseline; >1.5 - 3.0 x ULN	Creatinine Kinase >3.0 x baseline; >3.0 - 6.0 x ULN	Creatinine Kinase >6.0 x ULN	
Fibrinogen decreased	<1.0 - 0.75 x LLN; if abnormal, <25% decrease from baseline	<0.75 - 0.5 x LLN; if abnormal, 25 - <50% decrease from baseline	<0.5 - 0.25 x LLN; if abnormal, 50 - <75% decrease from baseline	<0.25 x LLN; if abnormal, 75% decrease from baseline; absolute value <50 mg/dL	Ranges defined for "abnormal" are applied only on values < LLN. Grade 0 will be assigned to values > ULN.
GGT increased	>ULN - 2.5 x ULN if baseline was normal; 2.0 - 2.5 x baseline if baseline was abnormal	>2.5 - 5.0 x ULN if baseline was normal; >2.5 - 5.0 x baseline if baseline was abnormal	>5.0 - 20.0 x ULN if baseline was normal; >5.0 - 20.0 x baseline if baseline was abnormal	>20.0 x ULN if baseline was normal; >20.0 x baseline if baseline was abnormal	Ranges defined for "abnormal baseline" are applied only if baseline > ULN. If baseline < LLN, then ranges for "normal baseline" are applied.
Haptoglobin decreased	<LLN	-	-	-	
Hemoglobin increased	Increase in >0 - 2 g/dL; Increase in >0 - 20 g/L	Increase in >2 - 4 g/dL; Increase in >20 - 40 g/L	Increase in >4 g/dL; Increase in >40 g/L	-	The increase indicates the level of increase above normal (above ULN). Applied as, e.g. grade 1 (g/dL): >ULN - ULN+2 g/dL; Added ranges in SI unit (g/L).

CTCAE Term	Grade 1	Grade 2	Grade 3	Grade 4	Janssen implementation notes
INR increased	>1.2 - 1.5; >1 - 1.5 x baseline if on anticoagulation; monitoring only indicated	>1.5 - 2.5; >1.5 - 2.5 x baseline if on anticoagulation; dose adjustment indicated	>2.5; >2.5 x baseline if on anticoagulation; bleeding	-	Concomitant therapy or clinical signs and symptoms are not taken into consideration for grading.
Lipase increased	>ULN - 1.5 x ULN	>1.5 - 2.0 x ULN; >2.0 - 5.0 x ULN and asymptomatic	>2.0 - 5.0 x ULN with signs or symptoms; >5.0 x ULN and asymptomatic	>5.0 x ULN and with signs or symptoms	“Asymptomatic” ranges are not taken into consideration for grading, i.e. worst case grading is applied.
Lymphocyte count decreased	<LLN - 800/mm ³ ; <LLN - 0.8 x 10e9/L	<800 - 500/mm ³ ; <0.8 - 0.5 x 10e9 /L	<500 - 200/mm ³ ; <0.5 - 0.2 x 10e9 /L	<200/mm ³ ; <0.2 x 10e9 /L	Added ranges in SI unit (x 10e9 /L).
Lymphocyte count increased	-	>4000/mm ³ - 20,000/mm ³ ; >4 - 20 x 10e9 /L	>20,000/mm ³ ; >20 x 10e9 /L	-	
Neutrophil count decreased	<LLN - 1500/mm ³ ; <LLN - 1.5 x 10e9 /L	<1500 - 1000/mm ³ ; <1.5 - 1.0 x 10e9 /L	<1000 - 500/mm ³ ; <1.0 - 0.5 x 10e9 /L	<500/mm ³ ; <0.5 x 10e9 /L	Both Neutrophils and segmented neutrophils are graded using these criteria.
Platelet count decreased	<LLN - 75,000/mm ³ ; <LLN - 75.0 x 10e9 /L	<75,000 - 50,000/mm ³ ; <75.0 - 50.0 x 10e9 /L	<50,000 - 25,000/mm ³ ; <50.0 - 25.0 x 10e9 /L	<25,000/mm ³ ; <25.0 x 10e9 /L	
Serum amylase increased	>ULN - 1.5 x ULN	>1.5 - 2.0 x ULN; >2.0 - 5.0 x ULN and asymptomatic	>2.0 - 5.0 x ULN with signs or symptoms; >5.0 x ULN and asymptomatic	>5.0 x ULN and with signs or symptoms	“Asymptomatic” ranges are not taken into consideration for grading, i.e. worst case grading is applied.
White blood cell decreased	<LLN - 3000/mm ³ ; <LLN - 3.0 x 10e9 /L	<3000 - 2000/mm ³ ; <2.0 x 10e9 /L	<2000 - 1000/mm ³ ; <1.0 x 10e9 /L	<1000/mm ³ ; <1.0 x 10e9 /L	
Metabolism and nutrition disorders					
Acidosis	pH <normal, but ≥7.3	-	pH <7.3	Life-threatening consequences	pH <normal is implemented as pH <LLN. Clinical signs and symptoms are not taken into consideration for grading.

CTCAE Term	Grade 1	Grade 2	Grade 3	Grade 4	Janssen implementation notes
Alkalosis	pH >normal, but ≤7.5	-	pH >7.5	Life-threatening consequences	pH >normal is implemented as pH >ULN. Clinical signs and symptoms are not taken into consideration for grading.
Hypercalcemia	Corrected serum calcium of >ULN - 11.5 mg/dL; >ULN - 2.9 mmol/L; Ionized calcium >ULN - 1.5 mmol/L	Corrected serum calcium of >11.5 - 12.5 mg/dL; >2.9 - 3.1 mmol/L; Ionized calcium >1.5 - 1.6 mmol/L; symptomatic	Corrected serum calcium of >12.5 - 13.5 mg/dL; >3.1 - 3.4 mmol/L; Ionized calcium >1.6 - 1.8 mmol/L; hospitalization indicated	Corrected serum calcium of >13.5 mg/dL; >3.4 mmol/L; Ionized calcium >1.8 mmol/L; life-threatening consequences	Clinical signs and symptoms are not taken into consideration for grading.
Hyperkalemia	Potassium >ULN - 5.5 mmol/L	Potassium >5.5 - 6.0 mmol/L; intervention initiated	Potassium >6.0 - 7.0 mmol/L; hospitalization indicated	Potassium >7.0 mmol/L; life-threatening consequences	Clinical signs and symptoms are not taken into consideration for grading.
Hypermagnesemia	Magnesium >ULN - 3.0 mg/dL; >ULN - 1.23 mmol/L	-	Magnesium >3.0 - 8.0 mg/dL; >1.23 - 3.30 mmol/L	Magnesium >8.0 mg/dL; >3.30 mmol/L; life-threatening consequences	Clinical signs and symptoms are not taken into consideration for grading.
Hypernatremia	Sodium >ULN - 150 mmol/L	Sodium >150 - 155 mmol/L; intervention initiated	Sodium >155 - 160 mmol/L; hospitalization indicated	Sodium >160 mmol/L; life-threatening consequences	Clinical signs and symptoms are not taken into consideration for grading.
Hypertriglyceridemia	Triglycerides 150 mg/dL - 300 mg/dL; 1.71 mmol/L - 3.42 mmol/L	Triglycerides >300 mg/dL - 500 mg/dL; >3.42 mmol/L - 5.7 mmol/L	Triglycerides >500 mg/dL - 1000 mg/dL; >5.7 mmol/L - 11.4 mmol/L	Triglycerides >1000 mg/dL; >11.4 mmol/L; life-threatening consequences	Clinical signs and symptoms are not taken into consideration for grading.
Hypoalbuminemia	Albumin <LLN - 3 g/dL; <LLN - 30 g/L	Albumin <3 - 2 g/dL; <30 - 20 g/L	Albumin <2 g/dL; <20 g/L	Life-threatening consequences; urgent intervention indicated	Clinical signs and symptoms are not taken into consideration for grading.

CTCAE Term	Grade 1	Grade 2	Grade 3	Grade 4	Janssen implementation notes
Hypocalcemia	Corrected serum calcium of <LLN - 8.0 mg/dL; <LLN - 2.0 mmol/L; Ionized calcium <LLN - 1.0 mmol/L	Corrected serum calcium of <8.0 - 7.0 mg/dL; <2.0 - 1.75 mmol/L; Ionized calcium <1.0 - 0.9 mmol/L; symptomatic	Corrected serum calcium of <7.0 - 6.0 mg/dL; <1.75 - 1.5 mmol/L; Ionized calcium <0.9 - 0.8 mmol/L; hospitalization indicated	Corrected serum calcium of <6.0 mg/dL; <1.5 mmol/L; Ionized calcium <0.8 mmol/L; life-threatening consequences	Clinical signs and symptoms are not taken into consideration for grading.
Hypoglycemia	Glucose <LLN - 55 mg/dL; <LLN - 3.0 mmol/L	Glucose <55 - 40 mg/dL; <3.0 - 2.2 mmol/L	Glucose <40 - 30 mg/dL; <2.2 - 1.7 mmol/L	Glucose <30 mg/dL; <1.7 mmol/L; life-threatening consequences; seizures	Clinical signs and symptoms are not taken into consideration for grading. Urine glucose is not graded.
Hypokalemia	Potassium <LLN - 3.0 mmol/L	Symptomatic with Potassium <LLN - 3.0 mmol/L; intervention indicated	Potassium <3.0 - 2.5 mmol/L; hospitalization indicated	Potassium <2.5 mmol/L; life-threatening consequences	“Symptomatic” ranges are applied for grade 2, grade 1 not assigned, i.e. worst case applied. Clinical signs and symptoms are not taken into consideration for grading of grade 3 and 4.
Hypomagnesemia	Magnesium <LLN - 1.2 mg/dL; <LLN - 0.5 mmol/L	Magnesium <1.2 - 0.9 mg/dL; <0.5 - 0.4 mmol/L	Magnesium <0.9 - 0.7 mg/dL; <0.4 - 0.3 mmol/L	Magnesium <0.7 mg/dL; <0.3 mmol/L; life-threatening consequences	Clinical signs and symptoms are not taken into consideration for grading.

CTCAE Term	Grade 1	Grade 2	Grade 3	Grade 4	Janssen implementation notes
Hyponatremia	Sodium <LLN - 130 mmol/L	Sodium 125-129 mmol/L and asymptomatic	Sodium 125-129 mmol/L symptomatic; 120-124 mmol/L regardless of symptoms Sodium <130-120 mmol/L	Sodium <120 mmol/L; life-threatening consequences	Clinical signs and symptoms are not taken into consideration for grading. Worst case (“<130-120 mmol/L” for grade 3 added by Janssen) is applied across grade 2/3 ranges: 120-129 mol/L assigned to grade 3, grade 2 not used.

* Grade 0 is assigned to a lab assessment when the lab test is described in the table, but the lab value is not assigned a grade 1 or higher.

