9.4.6. Safety Analyses

All safety analyses will be analyzed using the SAS population (refer to Section 9.3 for definition).

Adverse Events

The verbatim terms used in the eCRF by investigators to identify AEs will be coded using the Medical Dictionary for Regulatory Activities. Any AE occurring at or after the initial administration of study intervention is considered to be treatment-emergent. All reported treatment-emergent AEs will be included in the analysis. For each AE, the percentage of participants who experience at least 1 occurrence of the given event will be summarized by intervention group. In addition, comparisons between intervention groups will be provided if appropriate.

The following analyses of AEs will be used to assess the safety of participants:

- Frequency and type of AEs.
- Frequency and type of SAEs.
- Frequency and type of reasonably related AEs as assessed by the investigator.
- Frequency and type of AEs leading to discontinuation of study intervention.
- Frequency and type of infections, serious infections, and infections requiring oral or parenteral antimicrobial treatment.
- Frequency and type of AEs temporally associated with an infusion.
- Frequency and type of injection-site reactions.

Summaries, listings, datasets, or participant narratives may be provided through Week 24 and Week 60 by treatment intervention, for the above AEs, deaths, and severe AEs. Selected safety summaries will also be performed for participants of the LTE (Section 9.4.8).

Clinical Laboratory Tests

Laboratory data will be summarized by type of laboratory test over time, and by treatment intervention. CTCAE toxicity grades (specified in the SAP) will be used in the summary of laboratory data. Descriptive statistics will be calculated for each laboratory analyte at baseline and for observed values and changes from baseline at each scheduled timepoint.

The following summaries of clinical laboratory tests will be used to assess participant safety:

- Laboratory parameters and change from baseline in laboratory parameters (hematology and chemistry).
- Summary of maximum CTCAE toxicity grade for postbaseline laboratory values (hematology and chemistry).

Listings of participants with any abnormal postbaseline laboratory values of CTCAE Grade ≥ 2 will also be provided.

Vital Signs

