5.7.3. Additional Safety Assessments**5.7.3.1. Clinical Laboratory Tests**

Clinical laboratory tests will be displayed for the participants included in the safety analysis set.

Descriptive statistics and graphical displays will be presented for selected chemistry and hematology, laboratory tests at scheduled time points.

Change from baseline through Week 24 and Week 52 will be summarized for chemistry and hematology tests and displayed by intervention group. A box plot of change from baseline through Week 24 and Week 52 will be provided.

- **Hematology assessments** will include but are not limited to the following: hemoglobin, hematocrit, platelet count, total and differential White Blood Cell count, B-cell analysis.
- **Blood chemistry assessments** will include but are not limited to the following: chemistry panel (total and direct bilirubin, alanine aminotransferase, aspartate aminotransferase, alkaline phosphatase, albumin, total protein, calcium, phosphate, sodium, potassium, chloride, blood urea nitrogen/urea, and creatinine).

The National Cancer Institute's Common Terminology Criteria for Adverse Events (NCI-CTCAE; version 5.0) will be used in the summary of laboratory data (Grade 0-4). The proportion of participants with post-baseline values by maximum toxicity grade for clinical laboratory tests will be summarized by study intervention group. Participants with toxicity grades ≥ 2 will be listed.

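### The normal-range reset in SAP Appendix 10 overrides the table's own baseline-relative creatinine grades for values at or below ULN, so some in-range rises miss the maximum-grade table and the Grade 2 or higher listing

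*SAP*

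**What the plan says.** **The reset.** SAP Appendix 10 places a general rule above the grading table: "If a laboratory value falls within the grading as specified below but also within the local laboratory normal limits", then "the value is considered to be normal and will be reset to grade 0". No row is excepted.

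**The creatinine row.** The *Creatinine increased* row, in the same appendix, reads:

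- Grade 1: "Creatinine Kinase >ULN - 1.5 x ULN"
- Grade 2: "Creatinine Kinase >1.5 - 3.0 x baseline; >1.5 - 3.0 x ULN"
- Grade 3: "Creatinine Kinase >3.0 x baseline; >3.0 - 6.0 x ULN"

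Its implementation-note column is empty.

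**The outputs.** SAP 5.7.3.1 states: "The proportion of participants with post-baseline values by maximum toxicity grade for clinical laboratory tests will be summarized by study intervention group". It also lists participants with Grade 2 or higher, summarizes chemistry change from baseline by group, and provides a box plot. SAP 5.7 keeps all safety analyses for the CSR. Maximum toxicity grade is a named safety endpoint in Protocol Section 3 and SAP 1.1.

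**The concern.** A baseline-relative creatinine criterion is useful mainly for a participant with a low baseline, whose value can rise a good deal before it crosses ULN. That is the case in which the reset takes the grade away.

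This trial has reason to look at such rises, because the kidney is the target organ. Participants with good renal function can enter: Protocol 5.2 excludes only eGFR below 30, and the baseline table in SAP Appendix 3 has a category for eGFR of 90 or more. With fewer than 60 participants, one ungraded case could change how a small table reads.

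**Working it through.** The plan states no figure on this point, so there is none to reproduce. The check has two parts.

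**1. Is creatinine the only row affected?** The other rows with a baseline-relative arm, read with their implementation notes:

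| Row | When the baseline-relative arm applies | Can the reset remove that grade? |
|---|---|---|
| ALT, AST, ALP, GGT, bilirubin | Only if baseline is above ULN | No: a graded multiple of such a baseline is itself above ULN |
| Fibrinogen | Only for values below LLN | No: the value is already outside the range |
| INR | Depends on anticoagulation, and the note disregards concomitant therapy | Arm not used |
| Creatinine | No condition, no note | Yes, when the value is at or below ULN |

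**2. At which baselines does it happen?** Let *b* be baseline and *r* the fold rise. The table grades the rise if *r* > 1.5 (Grade 2) or *r* > 3 (Grade 3). The reset applies if *r* × *b* ≤ ULN, that is if *b* ≤ ULN / *r*. The risen value is taken to be above the lower limit of normal. The documents give no ULN, so 0.9 to 1.3 mg/dL is assumed.

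| Rise | Condition for reset | ULN 0.9 | ULN 1.1 | ULN 1.3 |
|---|---|---|---|---|
| Just above 1.5-fold | *b* < ULN / 1.5 | 0.60 | 0.73 | 0.87 |
| Doubling | *b* ≤ ULN / 2 | 0.45 | 0.55 | 0.65 |
| Just above 3-fold | *b* < ULN / 3 | 0.30 | 0.37 | 0.43 |

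Examples at an assumed ULN of 1.1 mg/dL:

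- 0.6 to 1.0 (1.67-fold): Grade 2 by the table, Grade 0 after the reset.
- 0.5 to 1.0 (2.0-fold): Grade 2, then Grade 0.
- 0.35 to 1.07 (3.06-fold): Grade 3, then Grade 0.
- 0.7 to 1.2 (1.71-fold): Grade 2, and it stays Grade 2 because 1.2 exceeds ULN. The ULN arm alone would give Grade 1, so here the baseline arm still does its work.

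**The case against.** The strongest reply is that the rule is deliberate. It foresees a value that is both graded and in range, and it says which prevails. That stands: this is a stated order of precedence, and a reader who infers that the two rules contradict each other goes too far. What remains is that the creatinine row's baseline arm operates only above ULN and no note says so, although the notes for the liver-enzyme, bilirubin and fibrinogen rows spell out their limits.

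A reader might also infer that renal deterioration would be hidden from the CSR. The documents do not support that:

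- Values above ULN keep their grade. The reset acts value by value, so another graded creatinine result still brings the participant into the table and listing.
- Group change-from-baseline summaries and box plots remain.
- Protocol 8.2.4 has investigators review laboratory results and record clinically relevant changes as adverse events, which are listed under SAP 5.7.2.
- The DMC reviews unblinded safety data.

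The group summaries do not identify the participant, and the adverse event route depends on the investigator's judgment. These outputs therefore reduce the gap without closing it.

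Nor does the complete renal response definition strengthen the point. Its eGFR component is met by a value of at least 60 or by no confirmed fall of 20% or more, so it accepts a relative decline when absolute function is preserved.

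Three cautions about the text also stand:

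- The cells of the row name *Creatinine Kinase*. Serum creatinine is inferred from the row heading and from the separate CPK row.
- Appendix 10 does not apply gray italic text, and that formatting cannot be checked in the extracted document. If the baseline arms were gray, in-range rises would be ungraded for that reason instead.
- The listing in Protocol 9.4.6 is worded for abnormal values, so an in-range value may never have been due there. The SAP listing and the maximum-grade table carry no such limit.

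**Conclusion.** The point holds for creatinine values at or below ULN. There the reset removes Grade 2 or Grade 3 assignments that the row makes, and the rise is missing from the maximum-grade table and the SAP's Grade 2 or higher listing. Creatinine is the only baseline-relative row where this happens.

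The size is known only as a condition on baseline: below about two thirds of ULN for a rise just above 1.5-fold, at or below half for a doubling, and below one third for a rise above 3-fold. The mg/dL figures rest on the assumed ULN range. Without a baseline creatinine distribution, the number of participants cannot be computed and may be small. The conclusion also rests on reading the row as serum creatinine and on its baseline arms being in force.

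This is a cheap improvement to safety reporting. It does not show that the safety analysis is unsound.

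**What to change.** In SAP Appendix 10, do one of the following:

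- add a sentence exempting the baseline-relative serum creatinine grades from the normal-range reset; or
- keep the reset and add a by-arm table and a participant listing of creatinine above 1.5 and above 3.0 times baseline, regardless of normal range. This option also works if the baseline arms turn out not to be applied.

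In the same edit, correct the *Creatinine Kinase* label. Also state which normal limits drive the reset: the rule refers to local limits, while Protocol 8.2.4 and Appendix 8 assign these tests to the central laboratory.

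The cost of the exemption is one sentence and one programming exception; the alternative costs one extra table and listing. The downside of the exemption is a few additional Grade 2 entries from modest absolute rises in participants with a low baseline. The reset stays in place for every other row.
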